## **2.2 Hypothesis to be tested/Exploratory study design:**

We hypothesize the intervention arm will have higher rates of biochemically confirmed self-reported tobacco use abstinence (preliminary efficacy; primary outcome) compared to the control arm at 3 month follow up.

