
CYP2A6 genotype-predicted phenotype (slow, intermediate, extensive) and other genetic variants of interest may be explored as co-variants in the analysis. Given the exploratory nature of the genetic analysis, we are likely underpowered to find significant association across numerous genetic co-variants, but these data may inform future studies designed to evaluate the relationship.

SHORT TITLE:

**27.2** Our proposed sample size [n=144 (96 treatment, 48 control)] is well within the recommendations for behavioral intervention development pilot trials based on what is feasible to recruit in our hospital and judged to be sufficient to evaluate efficacy (i.e., self-reported/biochemically verified abstinence) in a preliminary behavioral design trial. With respect to percentage reporting self-reported and/or biochemically confirmed abstinence at 3-mo follow up the margin of error (ME) around our observed outcomes depends on the observed proportion with the largest ME occurring when the proportion is 50%. Our sample size is sufficient to provide a ME of 10% (if the proportion is 50%) or less.

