Title: Development and Implementation of a Tobacco and ENDS Treatment Intervention for Adolescents and Young Adults in the Pediatric Hospital

Clinical Trial: NCT05936099

Date: August 30 2024

STATISTICAL DESIGN AND POWER

Aim 2: Evaluate preliminary efficacy and implementation outcomes of our tobacco and ENDS use intervention

Design: We will conduct a prospective, pilot trial with 3-month follow up to assess preliminary efficacy and implementation outcomes (Table 3). Hospitalized AYAs (n=144) with current (past 30-day) ENDS use (including those with co-use of cigarettes) will be randomized 2:1 to receive our novel intervention or control intervention that will consist of brief advice and printed quit line referral (see Figure 2). We will evaluate preliminary efficacy (i.e., 30-day self-reported abstinence with biochemical verification) as the primary outcome. We will also assess self-reported motivation and confidence to quit immediately post-intervention and at 3-month follow up and implementation outcomes (i.e. acceptability, feasibility, and fidelity).

Data Sources: AYAs: surveys, electronic health record; Parents/Guardians: surveys; Hospital Provider (i.e., [name]: survey, audio-recording of sessions; Health educator: survey, field notes, audio-recording of sessions

Assessments:

AYA Participants: We will use confidential, web-based surveys administered via Research Electronic Data Capture (REDCap) to capture AYA data pre- and post-intervention, 3-month follow up (Research Strategy Table 3 and 4, Appendix). The health educator will recruit, screen, consent, and randomize eligible participants. AYAs who decline to participate will be asked to provide age, sex, race and ethnicity to facilitate identification of participation bias. Randomization of consented participants will be stratified on sex and age using a 2:1 ratio within strata via computer generated assignment sequence placed in sequentially numbered sealed envelopes. *Control participants* will receive brief advice from the health educator regarding tobacco and ENDS use cessation and printed referral to a quit line. *Intervention participants* will receive the intervention developed in Aim 1, administered by the same health educator and [name]. All participants will complete a pre- and post-intervention survey and a 3-month survey sent via email, text message, and/or mailed paper survey so the research team is not directly involved in outcome data collection.

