AYA participants: We will use confidential, web-based surveys administered via Research Electronic Data Capture (REDCap) to assess post-intervention outcome measures including preliminary efficacy using previously validated survey questions to assess self reported 30-day abstinence and acceptability using 5-point

Parents/Guardians: We will use confidential, web-based surveys administered via Research Electronic Data Capture (REDCap) to assess post-intervention 5-point Likert scale implementation items among parents/guardians of AYA participants (Research Strategy Tables 3 and 4, Appendix).

Hospital Provider ([name]): We will use confidential, web-based surveys administered via REDCap to assess post-intervention 5-point Likert scale items and audio-recording of sessions to examine feasibility and fidelity (Research Strategy Table 3 and 4, Appendix).

Health Educator: We will use confidential, web-based surveys administered via REDCap to assess post-intervention 5-point Likert scale implementation items and will take field notes (Table 3 Research Strategy, Appendix). We will use field notes, audio-recording of sessions and survey items by the health educator to examine feasibility and fidelity.

Analysis:

We will use level of significance $\alpha=0.05$ and all analyses will be conducted using SAS v 9.4 (SAS Institute, Cary, NC, USA).

Measures and Statistical Analysis:

Participant demographics and clinical characteristics (e.g., age of initiation, nicotine dependence) will be assessed at baseline. The outcome measures, method of assessment, relevant stakeholders and associated outcome measures are depicted in Table 3 and sample survey items in Table 4.

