To assess *preliminary efficacy*, differences in self-reported and biochemically verified 30-day tobacco/ENDS use abstinence at 3-month follow up (primary outcome) will be analyzed using a generalized linear model assuming an underlying binomial distribution and logit link function to compare between study arms. Motivation and Confidence to quit will be analyzed using a repeated measures analysis of variance. Potential differential outcomes based on sex and demographic factors will be explored. Chi-square (categorical variables) and Wilcoxon Rank Sum (continuous variables) tests will be used to assess participation bias. For acceptability, we will calculate the proportion of AYA participants and parents/guardians in the intervention arm with mean ratings of satisfaction and acceptability of ≥ 4 on the 5-point Likert scale. In addition, frequencies and percentages will be used to describe the enrollment and session completion rate. For *feasibility* we will conduct thematic analysis of field notes and conduct simple descriptive analyses (means, frequencies, percentages) of the brief survey items completed by [name] and the health educator and session length data. *Fidelity* will be summarized utilizing similar descriptive analyses of the fidelity ratings (e.g., percentage of intervention steps completed; mean rating of key MI skill adherence). Potential differential outcomes based on sex and demographic factors will be explored. Chi-square (categorical variables) and Wilcoxon Rank Sum (continuous variables) tests will be used to assess participation bias.

Sample Size Our proposed *sample size* [$n=144$ (96 treatment, 48 control)] is well within the recommendations for behavioral intervention development pilot trials based on what is feasible to recruit in our hospital and judged to be sufficient to evaluate efficacy (i.e., self-reported/biochemically verified abstinence) in a preliminary behavioral design trial.^{63,64} With respect to percentage reporting self-reported and/or biochemically confirmed abstinence at 3-mo follow up the margin of error (ME) around our observed outcomes depends on the observed proportion with the largest ME occurring when the proportion is 50%. Our sample size is sufficient to provide a ME of 10% (if the proportion is 50%) or less. A study fully powered to determine efficacy will be the focus of an R01 hybrid implementation trial informed by this study.

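### The primary logit model has no named test, interval or sparse-cell rule; if control abstinence is about 5% or lower, the odds ratio may not be finite and the unnamed test can decide the result

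*SAP*

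**What the plan says.** The SAP (Measures and Statistical Analysis) and Protocol 27.1 describe the primary comparison in the same words: abstinence "will be analyzed using a generalized linear model assuming an underlying binomial distribution and logit link function to compare between study arms". The SAP (Analysis) adds a 0.05 significance level and that "all analyses will be conducted using SAS v 9.4". No SAS procedure, test statistic, interval method, covariate list or sparse-data fallback is given.

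Protocol 27.2 gives the sample size as "n=144 (96 treatment, 48 control" participants, and the SAP (Design) says that patients "will be randomized 2:1 to receive our novel intervention or control intervention". Protocol 2.2 states a comparative hypothesis, that the "intervention arm will have higher rates of biochemically confirmed self-reported tobacco use abstinence".

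The sample size text gives no expected rate, effect size or power. It says only that "the margin of error (ME) around our observed outcomes depends on the observed proportion", with the "largest ME occurring when the proportion is 50" per cent.

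**The concern.** A control counts as a success only after reporting 30 days without tobacco or ENDS at 3 months and having that report confirmed by a saliva test done at a distance. The control arm gets short counselling and a printed quit-line contact. With 48 such participants, a count of zero or one is possible.

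Two things then go wrong with an ordinary maximum-likelihood logit fit. With no control success the odds ratio has no finite estimate, whichever test is used. In sparse tables the Wald, likelihood-ratio and score tests from the same model also give very different p-values. As the plan names none of them, the primary result could turn on a choice made after the data are seen. The tables affected include those most favourable to the intervention. A pilot's main product is an estimate for the next trial, so it should be protected against this.

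**Working it through.** **Inputs from the documents.** 96 intervention and 48 control participants; significance level 0.05; binomial model with logit link.

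**Assumptions.** Two-sided testing, since sidedness is not stated. True abstinence rates from 2% to 40%, since none is given. An unadjusted model, since the SAP lists no covariates. As no dropout rate is given, 36 analysed controls (25% loss) serves as a sensitivity case.

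**Step 1: the plan's own figure.** The half-width at a proportion of 50% is 1.96 × √(0.25/n). For n = 144 it is 8.2%, for n = 96 it is 10.0%, and for n = 48 it is 14.1%. The stated 10% reproduces for the whole sample and for the intervention arm. It describes a single proportion and says nothing about the comparison between arms.

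**Step 2: chance of no abstinent control, (1 − p)ⁿ.**

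| True control rate | 48 controls | 36 controls |
|---|---|---|
| 2% | 0.98⁴⁸ = 38% | 0.98³⁶ = 48% |
| 5% | 0.95⁴⁸ = 8.5% | 0.95³⁶ = 16% |
| 10% | 0.90⁴⁸ = 0.6% | 0.90³⁶ = 2% |
| 15% | 0.85⁴⁸ = 0.04% | 0.85³⁶ = 0.3% |

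**Step 3: what the model returns with 0/48.** For 12/96 v 0/48 the ordinary fit gives a log odds ratio of about 21.6 with a standard error of about 11,469, which is a failure to converge to any finite value. The Wald p-value is 0.998, while the score p-value is 0.011. The risk difference is 12/96 − 0/48 = 12.5 points (Miettinen-Nurminen 95% CI 4.7 to 20.6). In the unadjusted two-arm case Firth's method amounts to adding 0.5 to each cell, so its odds ratio is finite: (12.5 × 48.5)/(84.5 × 0.5) = 14.3.

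With 0/48 controls, the smallest intervention count that gives p < 0.05 is:
- likelihood ratio: 5/96
- score or Firth: 8/96
- Wald: none, however many abstain

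At 6/96 v 0/48, for example, p is 0.025 by likelihood ratio, 0.077 by score, 0.088 by Firth and about 1 by Wald.

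**Step 4: true size at nominal 5%.** This is an exact sum over all 97 × 49 possible tables with the same rate in both arms. A zero cell counts as non-rejection for Wald.

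| Common rate | Wald | Likelihood ratio | Score | Firth |
|---|---|---|---|---|
| 2% | 0.2% | 5.8% | 4.1% | 1.6% |
| 5% | 1.9% | 7.8% | 3.9% | 3.7% |
| 10% | 3.1% | 5.8% | 4.8% | 4.4% |
| 15% | 3.9% | 5.4% | 5.1% | 5.0% |
| 20% | 4.4% | 5.3% | 5.0% | 5.0% |

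**Step 5: power, 96 v 48, by the same sum.**

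| Control v intervention | Wald | Score | Firth |
|---|---|---|---|
| 3% v 15% | 31% | 64% | 64% |
| 5% v 15% | 25% | 43% | 43% |
| 5% v 20% | 59% | 73% | 73% |
| 10% v 25% | 55% | 59% | 59% |
| 15% v 35% | 73% | 74% | 74% |
| 20% v 40% | 68% | 70% | 69% |

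**The case against.** Three objections carry weight.

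*The plan does not specify a Wald test.* A reader might infer a badly conservative primary test, because Wald p-values are common output for logistic models. The documents do not support that. They name a model and a software version only. The same model allows a likelihood-ratio test, which errs the other way at low rates, and a score test, which for a single arm term is the ordinary Pearson test and behaves well. So the defect is an unspecified test, not a conservative one. Leaving it open is still a weakness, because step 3 shows that the choice can decide the result.

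*The control rate is unknown.* Any use in the past 30 days qualifies, so occasional users are eligible, and control abstinence might be well above 5%. From about 15% upward almost nothing is at stake. This stands, and it makes the point conditional. It does not remove the need for a rule, since the documents give no rate that excludes the low range.

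*This is a pilot.* The SAP defers a fully powered efficacy test to a later trial, so lost power is not measured against any target that the plan set. That lowers the stakes. The plan nevertheless states a comparative hypothesis and a significance level.

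Two other strong readings should be resisted. One is that the sample size section planned precision for a difference between arms which the analysis then never estimates. The margin of error there concerns an observed proportion, so no such difference was planned and dropped. The other is that the comparison as a whole becomes inestimable. With a zero cell only the maximum-likelihood odds ratio is lost. The arm proportions, their difference and the likelihood-ratio and score p-values remain available.

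**Conclusion.** The point holds as a conditional gap in the specification that is worth closing. If true control abstinence is about 5% or lower, there is a material chance of an odds ratio that is not finite, and the conclusion can depend on a test that the plan does not name. Near 10% the effect is modest: about 4 points of power between Wald and score or Firth at 10% v 25%. From about 15% it is negligible. These figures rest on assumed rates, two-sided testing and an unadjusted model; none comes from the documents. Loss to follow-up makes a zero control count more likely. The matter should be settled before the data are seen, but it does not threaten the trial.

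**What to change.** In the SAP (Measures and Statistical Analysis) and Protocol 27.1:

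1. Keep the logistic model, but fit it by Firth penalised likelihood. Name the penalised likelihood-ratio test and the profile-likelihood 95% interval, and include the sex and age stratification factors.
2. Report the two arm proportions and their risk difference with a Miettinen-Nurminen (score) 95% interval, stratified where cell counts allow.

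Both methods are available in SAS 9.4, which the plan already names. The cost is a few sentences of SAP and protocol wording and a little more analysis, with no change to conduct or sample size. Firth is itself conservative in the sparsest case (size 1.6% at a common 2% rate). In the unadjusted comparison it loses no power against Wald at higher rates (69% v 68% at 20% v 40%). The adjusted version was not enumerated.

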Hospital Staff will be asked to complete a post-intervention survey and interview conducted by the health educator to assess acceptability and disruption of the intervention, it will take approximately 10 minutes, the only PHI that will be collected is to compensate them and will include no sensitive data.

Participant demographics and clinical characteristics (e.g., age of initiation, nicotine dependence) will be assessed at baseline. Preliminary efficacy will be assessed via self-reported 30-day point prevalence tobacco/ENDS abstinence using the timeline follow-back method at 3-month follow-up. To obtain a biochemically verified outcome and to encourage accurate self-reporting we will assess salivary cotinine via mailed samples from all participants (not currently on NRT) who report abstinence. We will assess this by either mailing a saliva specimen home collection kit to then be return mailed (pre

addressed and paid) to our study team or we will also offer the option of completing a home saliva cotinine test which do not require return mailing. For this option home saliva cotinine tests will be mailed to the participant. The study team will then schedule a secure Microsoft Teams video call to witness saliva test completion and results or photos of the test results can be emailed at a convenient time to [[contact]](mailto:[contact]) . Although accurate verification will not be possible with participants who are occasional users or those on NRT, this will also allow us to evaluate the feasibility of confirming abstinence by collecting saliva specimens by mail or completing witnessed (via Microsoft Teams secure video or securely emailed photos) home saliva cotinine tests in this population which will be informative for future studies with daily ENDS users. Secondary efficacy outcomes will include self-reported motivation and confidence to quit immediately post-intervention and at 3-month follow up. We will assess acceptability with the overall intervention and intervention components via survey immediately post intervention (AYAs and parents) and at 3 month follow-up (AYAs). We will also explore our secondary objective by obtaining a voluntary saliva or salvage leftover blood samples at baseline from all participants to assess genotyping the impact of individual-level factors (e.g., CYP2A6 genotype, nicotine metabolite ratio, sex) at baseline with our primary outcome (past 30 day ENDS use abstinence).

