## 11.0 Follow-up

- All AYA participants (both control and intervention arms) will be asked to complete a follow-up Survey at 12 weeks (completion window 10-14 weeks).
- AYA participants will receive an email and/or text via Twilio inviting them to complete the follow-up survey using a weblink provided. We will send up to 2 emails and/or 2 text reminders, as needed. If by

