## SHORT TITLE:

week 13 the participant has not completed the follow-up survey, a study team member will call them using the phone number(s) provided to remind them about the survey (maximum number of phone calls = 3). If needed at the time of the call, the follow-up survey weblink will be sent via email and/or text via Twilio.

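### Motivation and confidence to quit: the repeated measures analysis is left unspecified, so a complete-case version could discard observed post-intervention scores; separately, no stated model includes the randomisation strata

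*SAP*

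**What the plan says.** Protocol 5.1 defines the outcomes: "Secondary efficacy outcomes will include self-reported motivation and confidence to quit immediately post-intervention and at 3-month follow up". Table 3 in Protocol 27.1 and the SAP give the same two times.

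The whole analysis plan for them is one sentence, in the SAP under Measures and Statistical Analysis and again in Protocol 27.1: "Motivation and Confidence to quit will be analyzed using a repeated measures analysis of variance". On software, the SAP says that "all analyses will be conducted using SAS v 9.4". It names no procedure.

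On follow-up, Protocol 11.0 states: "All AYA participants (both control and intervention arms) will be asked to complete a follow-up Survey at 12 weeks". Reminders come first; then, if by week 13 "the participant has not completed the follow-up survey, a study team member will call them", up to three times. No expected response rate is given.

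On allocation, the SAP (Assessments) states: "Randomization of consented participants will be stratified on sex and age using a 2:1 ratio within strata". The age cut-point is not given. In the analysis of outcomes, sex and demographic factors appear only as something to explore for differential outcomes.

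On baseline, the SAP has a survey before the intervention: "All participants will complete a pre- and post-intervention survey and a 3-month survey sent via email". Protocol 5.1 says "Participant demographics and clinical characteristics (e.g., age of initiation, nicotine dependence) will be assessed at baseline". Neither says whether motivation and confidence are scored at that point.

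**The concern.** The phrase covers two different analyses. The classical form uses one row per participant and needs both scores, so a participant without the 3-month survey leaves the analysis altogether, including the post-intervention score. A likelihood-based mixed model for repeated measures keeps every observed score. SAS 9.4 can do either. The two use different participants for the immediate arm comparison, and the plan does not say which is meant or which contrast will be reported.

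Incomplete pairs are foreseeable. The 3-month survey is remote and the Protocol plans for chasing non-responders. Participants who turn 18 meet a reconsent step inside that survey (Protocol 20.2). Surveys are linked over time by a code that the participant creates (Protocol 23.1). What is at stake is precision at the post-intervention time, and a choice of method that could otherwise be made after the data are seen.

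The strata are a separate matter. Randomisation is balanced on sex and age, but no model uses them. Exploring subgroup differences is not adjustment. What is at stake there is some efficiency.

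**Working it through.** **Inputs from the documents.** 96 intervention and 48 control (SAP, Sample Size; Protocol 27.2); α = 0.05 (SAP, Analysis), taken as two-sided; scores post-intervention and at 3 months.

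**Assumptions.** All 144 give a post-intervention score. 3-month loss is 10%, 20% or 30%, equal in both arms and unrelated to scores. The SD is the same in both arms. The correlation between the two scores is r = 0.5. Sex and age explain a share R² of the score variance. The documents give none of these.

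**The plan's own figure.** The only precision stated is a margin of error of 10% or less for an abstinence proportion of 50%. 1.96 × √(0.25/n) gives 8.17% at n = 144, 10.00% at n = 96 and 14.14% at n = 48. So it reproduces for the whole sample and for the intervention arm, but not for the control arm alone. It concerns the primary outcome. No figure is given for motivation or confidence.

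**Step 1: post-intervention difference.** With f the fraction retained, the half-width in SD units is 1.96 × √(1/(96f) + 1/(48f)). At f = 1 this is 1.96 × √0.03125 = 0.346. Complete-case results:

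| Assumed loss | Post-intervention scores dropped | Half-width, complete case | Half-width, all scores | Widening, 1/√f |
|---|---|---|---|---|
| 10% | 144 × 0.1 ≈ 14 | 0.365 | 0.346 | +5% |
| 20% | 144 × 0.2 ≈ 29 | 0.387 | 0.346 | +12% |
| 30% | 144 × 0.3 ≈ 43 | 0.414 | 0.346 | +20% |

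**Step 2: 3-month difference.** The missing 3-month scores are gone under either method. The mixed model recovers only what the earlier score predicts: half-width = complete-case half-width × √(1 − r²(1 − f)).
- 20% loss: 0.387 × √(1 − 0.25 × 0.2) = 0.378, a gain of about 0.01 SD.
- 30% loss: 0.414 × √(1 − 0.25 × 0.3) = 0.398, a gain of about 0.02 SD.

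**Step 3: adding sex and age.** With q covariate degrees of freedom, the variance ratio, adjusted to unadjusted, is (1 − R²) × (1 + q/(N − 2 − q − 1)).
- R² = 0: 1 + 2/139 = 1.014 (N = 144, q = 2); 1 + 3/138 = 1.022 (N = 144, q = 3); 1 + 3/95 = 1.032 (N = 101, q = 3). The cost is about 1% to 3%.
- Break-even: R² = 1 − 1/1.014 ≈ 1.4% up to 1 − 1/1.032 ≈ 3.1%, so roughly 1.5% to 3%.
- R² = 5%, N = 144, q = 2: ratio 0.964, and the half-width goes from 0.346 to 0.340. R² = 10%: ratio 0.913, half-width 0.331.

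**The case against.** The strongest reply is that no data loss has been shown. The plan names neither a complete-case rule nor a procedure, and repeated measures can be fitted in PROC MIXED. Protocol 24.1 keeps data collected before a withdrawal for analysis, which points towards using observed scores. This stands in part. A reader might infer that the plan will discard scores; the documents do not support that, only that the wording permits it. But 24.1 covers withdrawal rather than an unreturned survey, and it sets no model, so the ambiguity remains.

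A reader might also infer that a mixed model takes care of the strata. It does not. Sex and age must be added as terms, and a classical analysis could include them equally well. Their omission costs some efficiency; nothing here shows bias from it. The gain is small and turns into a small loss if they explain almost nothing.

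A further tempting inference is that the arm differences would be biased. One can construct such cases, for example loss in the control arm only that depends on the score. The documents give no attrition rate or pattern, and describe invitations and reminders without distinction by arm. Such cases carry no weight in the conclusion. Nor would a mixed model remove bias if loss depended on the unseen 3-month score.

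Finally, if the pre-intervention survey carries these items, the authors may intend three repeated measures. That is a fair point about the replacement wording, because Table 4 and the Appendix were not available for this review. The classical form would still drop a participant with any score missing.

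**Conclusion.** The point holds as a gap in specification. The sentence permits a complete-case analysis that, at assumed losses of 10% to 30%, would widen the post-intervention half-width from 0.35 SD to between 0.37 and 0.41 SD by setting aside scores already collected. At 3 months the method makes little difference to precision: 0.01 to 0.02 SD at 20% to 30% loss and correlation 0.5. Separately, the stratification factors are in no stated model; adjusting for them changes variance by a few per cent in either direction unless they explain appreciably more than about 3% of it.

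Importance is minor. These are secondary outcomes of a pilot for which no power or precision is claimed, and the SAP leaves the fully powered test to a later trial. The primary abstinence analysis is not touched. Loss rates, correlation and R² are all assumptions.

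**What to change.** Replace the sentence in the SAP and in Protocol 27.1 with text such as:

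*Motivation and confidence to quit will each be analysed with a linear mixed model (SAS PROC MIXED, unstructured covariance) using all available post-intervention and 3-month scores, with fixed effects for arm, time and arm-by-time, and for sex and age in the form used for stratification. The arm difference with its 95% CI will be reported at each time. The model assumes that loss depends only on observed data; it does not remove bias if loss depends on the unobserved 3-month score.*

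Before finalising, confirm whether the pre-intervention survey collects the motivation and confidence items. If it does, add the baseline score as a covariate.

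The cost is one replaced sentence in each document, with software already named and no new data, visits or participants. The statistical downside is the 1% to 3% rise in variance if sex and age explain nothing.
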